8 TOXICITIES AND DOSEAGE MODIFICATION

N/A

This study will utilize the CTCAE (NCI Common Terminology Criteria for Adverse Events) Version 5.0 for adverse event and serious adverse event reporting.

8.1 **Dose Modifications** N/A

8.2 Supportive Care

8.2.1 All supportive measures consistent with optimal patient care will be given throughout the study.

9 STUDY CALENDAR

			W	eek	(+/·	- 2 d	lays	5)			Week (+/- 7 days)		
Examination	Screenin g ¹	Baseline ^{1,} 2 Day 1	1	2	3	4	5	6	7	8	9	End of study ⁵	22
Informed consent	Χ												
Eligibility criteria	X												
Concomitant medications	X											X	
Questionnaires ³													
• CIPN-20	X											X	X
• BPI		X										X	X
CIPN-R-ODS		X										X	X
• MAIA-2		X										X	X
• Demographics		X											
Acupuncture treatment (AT) ⁴				X X	X X	X	X	X	X	X	X		
fMRI ⁶			X									X	

¹ Screening visit and Baseline visit can occur on the same day.

- ² Day 1 (Baseline) should occur within 2 weeks of the screening visit.
- ³ Questionnaires include: (See Appendices).
- ⁴ Acupuncture treatment (AT) will occur at the Wellness & Integrative Health Center at HCI. Twice a week treatments will occur within 4 business days.
- ⁵ End of study visit should occur within one week of final acupuncture treatment.
- ⁶ Must be within 9 days of baseline visit. If participant prefers, first study fMRI can be same day as first AT treatment.

10 STUDY PROCEDURES

This study will enroll female patients who have completed treatment with either paclitaxel or docetaxel at least three months prior. Paclitaxel is a neurotoxic chemotherapy known to cause CIPN. Docetaxel is also a neurotoxic chemotherapy known to cause CIPN. Patients must have experienced at least one month of altered sensation in feet (with or without

presence in one or both hands) and/or pain with a score of greater than or equal to 20 for CIPN on the sensory subscale of the CIPN-20. We will commence recruitment 3 months after patients have completed their last chemotherapy dose.

Patients will be recruited from the Huntsman Cancer Center Oncology Clinics in collaboration with their oncologists.

For this study, enrollment will be limited to patients with breast, ovarian, cervical, endometrial, or uterine cancer with CIPN and completed chemotherapy treatments.

Visits:

Screening Visit:

Potentially eligible subjects will be scheduled for a screening visit. After informed consent is obtained, the SC will review and confirm inclusion/exclusion criteria. The SC will take a brief medical, history and administer the CIPN-20 questionnaire. If all inclusion and exclusion criteria are fulfilled, the subject will be scheduled for a baseline visit. This visit may occur on the same day as screening, but must occur within 2 weeks of study screening visit. If the participant has received treatment outside of University of Utah Health a medical record release form will be initiated and submitted as appropriate.

Baseline Visit:

Patients diagnosed with breast, ovarian, cervical, endometrial, or uterine cancer who will be treated with paclitaxel or docetaxel chemotherapy associated with CIPN will undergo a number of questionnaires. The patient will then be enrolled in the study and scheduled in the Wellness Center for acupuncture therapy (AT). All participants will be scheduled for fMRI, which must occur within nine days after baseline.

Participants will undergo study interview and fMRI within 9 days after baseline following enrollment.

Clinical data including current medications and medical history and fall rates will be gathered. Questionnaires (BPI, CIPN-20, CIPN-R-ODS, MAIA-2, Demograhpics) will be completed in person or emailed to patients via REDCap. Reminder calls and AT appointments will be scheduled by HCI Wellness and Integrative Health Center personnel in conjunction with a SC. The SC will aid participants in scheduling fMRI appointments online. AT treatments will occur within 7 days/4 business days in general. If participant prefers the first study fMRI and first AT appointment can occur same day, with the fMRI procedure occurring prior to AT treatment.

Follow up Visits:

Participants will receive 10 sessions of AT: twice per week for 2 weeks, thereafter once per week for six weeks, with a total of 10 treatments during a two-month course. Each session will last 45-60 minutes, with acupuncture needles retained 30-40 minutes. A minimum of 8 treatments must be received by each participant with no more than 9 days' gap between weekly treatments permitted (sessions 5-10). Concurrent medications are allowed as prescribed and will be tracked in the study and analyzed as potential confounders.

Final Visit:

Participants will undergo examination within one week of AT completion. This will include the fMRI scan and questionnaires. Compensation for participation will be offered at this visit.

Procedures:

Measures: Questionnaires will be completed in person or emailed to patients via REDCap at baseline and study conclusion, as well as at a 3-month follow-up. *Primary Endpoints:* Mean enrollment, percentage completion rate of all study procedures, frequency count of serious adverse events, and percentage of enrolled participants completing questionnaires will be calculated. Data will be collected via REDCap, stored in the Research Subject Registry (RSR) and analyzed with SPSS.

Additional measures to be collected: CIPN-20: This measure includes questions about tingling, numbness, painful numbness, cramps, balance, temperature intolerance, grasping items, ankle flexion weakness and leg weakness. CIPN-R-ODS (a validated measure of quality of life specific to CIPN), will be used to assess impact on function, BPI to assess pain and Multidimensional Assessment of Interoceptive Awareness (MAIA-2) to assess mind-body awareness. We will also collect *demographic* information including age, marital status, race and ethnicity. Related medical history and current medications information will be collected.

Acupuncture therapy (AT): AT will be delivered onsite at HCI in the Linda B. and Robert B. Wiggins Wellness & Integrative Health Center. AT will be delivered twice per week for two weeks and then weekly for six weeks by [name], DAOM, a Licensed Acupuncturist who has over five years' clinical experience treating persons with cancer, or another Licensed Acupuncturist in the Wellness & Integrative Health Center. Each session will last 45-60 minutes, with acupuncture needles retained 30-40 minutes. A minimum of 8 treatments must be received by each participant.

Functional MRI (fMRI) to be conducted within 9 days after baseline and within 1 week of final AT session. fMRI scans will be conducted at Imaging and Neuroscience Center (INC) in Research Park. Imaging will consist of structural brain imaging (MP2RAGE), task fMRI, and resting-state fMRI connectivity. Task fMRI will consist of a mental imagery task with a 20-second block design wherein patients will alternate between concentration on a part of their body where they experience pain and a part of their body where they do not experience pain, prompted by visual cues. We will provide gift cards for \$25 after the completion of the second fMRI.

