	feasibility data will consist of calculating
	frequencies and percentages Analysis of
	questionnaires will consist of within-

group pre/post analysis with student t-test and chi square with significance will be set at .05 and two-tailed hypotheses.
Sample Size Estimation: A sample size of 25-30 participants is ideal for a pilot feasibility study ¹ . However, we are recruiting only 20 participants due to funding constraints.

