5.1 Inclusion Criteria Yes/No (Response of "no" = patient ineligible)

- 5.1.1 _____ Female age 18 or older.
- 5.1.2 Histologically proven breast, uterine, cervical or ovarian cancer of any stage.
- 5.1.3 Received either (1) a Paclitaxel treatment dose of at least 480 mg/m² paclitaxel as a single or combination agent or (2) a Docetaxel treatment dose of at least 150 mg/m² docetaxel as a single or combination agent. Treatment must be completed at least 3 months prior to enrollment.
- 5.1.4 Eligible patients report at least 1 month of altered sensation and/or pain in the feet (with or without presence in one or both hands) with a score of greater than or equal to 20 for CIPN on the sensory subscale of the CIPN-20 (scale 0-100).

5.1.5. _____ Able to provide informed consent and willing to sign an approved consent form that conforms to federal and institutional guidelines.

5.1.6. ECOG status of 0 (asymptomatic), 1 (symptomatic but completely ambulatory) or 2 (symptomatic, <50% in bed during the day).

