6 STRATIFICATION FACTORS N/A

7 TREATMENT PLAN

7.1 Administration Schedule

Twenty participants will be enrolled. The manualized acupuncture treatment (AT) intervention will be designed by [name] and [name] and administered by [name] and members of Huntsman acupuncture team. Ten sessions of AT will be delivered: twice per week for 2 weeks, thereafter once per week for six weeks, with a total of 10 treatments during a two-month course. Each session will last 45-60 minutes, with acupuncture needles retained 30-40 minutes. A minimum of 8 treatments must be received within the acupuncture treatment window. Concurrent medications are allowed as prescribed and will be tracked in the study and analyzed as potential confounders.

Participants in the study will undergo study interview and fMRI at the following two time points: within 9 days after baseline following enrollment and within one week of acupuncture treatment completion. Clinical data including current medications and medical history and fall rates will be gathered during the baseline and study conclusion. Questionnaires will be completed in person or emailed to patients via REDCap at baseline and study conclusion, as well as at a 3-month follow-up. Reminder calls and AT appointments will be scheduled by HCI Wellness and Integrative Health Center personnel in coordination with the study coordinator (SC). The SC will aid participants in scheduling fMRI with an online scheduling system.

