12 STATISTICAL CONSIDERATIONS

Data will be collected via REDCap and analyzed with SPSS. Missing data will be handled with imputation of the median value of all available data for each individual item.¹⁹

Demographics: Analysis of demographic data will consist of calculating means, standard deviations, frequencies, and proportions. Demographic information to include: age, marital status, race and ethnicity, current medications and medical history.

Feasibility data: will be analyzed by calculating frequency and percentages, specifically:

- **Recruitment** frequency count (enrollment of 20 women, average of 2 eligible women per month to participate in the trial, identification of appropriate recruitment strategies, the appropriateness of eligibility criteria),
- **Retention** frequency and percentage (70% or more participants comply with 8 or more AT sessions and complete both fMRI scans)
- Safety frequency count (zero serious adverse events directly related to AT)
- **Questionnaire completion** frequency and percentage (70% or more enrolled participants complete at least 80% of questions at all protocol-directed time points).

Questionnaires: analyses will consist of student t-test and chi square computations according to the type of data.

- CIPN-20
- CIPN-R-ODS
- BPI
- Multidimensional Assessment of Interoceptive Awareness (MAIA-2)

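### The calendar omits the baseline CIPN-20 that Section 10 lists, and no section names the 'pre' score; if the calendar is followed, the entry score becomes 'pre' and the CIPN-20 change is biased toward improvement

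*Combined protocol and SAP*

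**What the plan says.** **When CIPN-20 is given.** At the Screening Visit, Section 10 states: "The SC will take a brief medical, history and administer the CIPN-20 questionnaire". Criterion 5.1.4 admits women "with a score of greater than or equal to 20 for CIPN on the sensory subscale of the CIPN-20 (scale 0-100"). For the Baseline Visit, Section 10 names CIPN-20 again: "Questionnaires (BPI, CIPN-20, CIPN-R-ODS, MAIA-2, Demograhpics) will be completed in person or emailed to patients via REDCap". Two other places ask for questionnaires at baseline without naming each one: Section 7.1 ("via REDCap at baseline and study conclusion, as well as at a 3-month follow-up") and the Measures paragraph of Section 10 ("Measures: Questionnaires will be completed in person or emailed to patients via REDCap at baseline and study conclusion").

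The Section 9 calendar differs. Its CIPN-20 row is marked at Screening, End of study and week 22. The BPI, CIPN-R-ODS and MAIA-2 rows are marked at Baseline, End of study and week 22. Footnote 1 adds: "Screening visit and Baseline visit can occur on the same day".

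**How it is analysed.** The Study Summary plans a within-"group pre/post analysis with student t-test and chi square with significance will be set at .05 and two-tailed hypotheses". For the questionnaires, Section 12 says only that "analyses will consist of student t-test and chi square computations according to the type of data". Objective 1.2.2 refers to the period before AT without naming a visit. No section says which CIPN-20 is 'pre', or whether the sensory subscale or the total is tested.

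**The concern.** Site staff cannot follow both the calendar and the Baseline Visit text. The choice affects the analysis. Under the calendar, the only pre-treatment CIPN-20 is the score that decided entry. A woman whose score happened to be high that day gets in, and one whose score happened to be low does not. The admitted group's entry mean therefore contains positive measurement error, and that error will not recur at End of study. The score is expected to fall even if nothing has changed, and a single-arm study has nothing to set that fall against.

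The CIPN-20 result under objective 1.2.2 is at stake. Section 2 says the pilot is to lay the ground for a randomized trial, so an inflated change could carry into its planning. The discrepancy also touches the definition of a primary endpoint. Section 12 counts questionnaire completion over all time points that the protocol directs, and whether a baseline CIPN-20 is one of them depends on which passage is followed.

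**Working it through.** **1. The passages side by side**

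| Place | CIPN-20 at screening | CIPN-20 at baseline |
|---|---|---|
| Section 9 calendar | marked | not marked |
| Section 10, Screening Visit | named | – |
| Section 10, Baseline Visit | – | named |
| Section 7.1; Section 10, Measures | – | questionnaires in general |
| Study Summary, 1.2.2, Section 12 | 'pre' score not defined | 'pre' score not defined |

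The three rows below CIPN-20 in the calendar are all marked one column to the right of it, so a broken table is an unlikely explanation.

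**2. Inputs.** From the documents: cut-off 20 on a 0–100 sensory scale (5.1.4), N=20 (4.3), two-sided .05 (Study Summary), one arm. For a smaller analysed sample I use n=14, which is the 70% retention target applied to 20. The plan has no figure of its own to reproduce: N is set by budget, and no mean, SD, reliability or power is given. Assumed: screened-pool mean m of 20 to 40, SD s of 15 or 20, reliability r of 0.7 to 0.9, normal true score plus independent error, no true change.

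**3. Expected fall if the entry score is 'pre'.** With z = (20 − m)/s, admitted women exceed the pool mean by s·φ(z)/(1 − Φ(z)). A share (1 − r) of that excess is error, so

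fall = (1 − r)·s·φ(z)/(1 − Φ(z)).

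Rejection rates come from a simulated paired t-test with 40,000 runs per setting.

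| m, s, r | Excluded by cut-off | Fall (points) | Rejection n=20 | Rejection n=14 |
|---|---|---|---|---|
| 20, 20, 0.7 | 50% | 0.3 × 20 × 0.3989/0.5 = 4.79 | 28.0% | 20.8% |
| 25, 20, 0.8 | 40% | 0.2 × 20 × 0.3867/0.5987 = 2.58 | 14.5% | 11.2% |
| 40, 20, 0.7 | 16% | 0.3 × 20 × 0.2420/0.8413 = 1.73 | 7.8% | 6.8% |
| 40, 15, 0.9 | 9% | 0.1 × 15 × 0.1640/0.9088 = 0.27 | 5.5% | 5.1% |

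In the first two rows nearly all rejections are toward improvement. Bounding the score at 0–100 in steps of 100/27 (nine items scored 1 to 4, linear rescaling assumed) changes little: 4.73, 2.63 and 0.29 points for rows 1, 2 and 4. The upper end depends on the range chosen. Allowing a reliability of 0.6 raises it to 6.4 points and about 36%.

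**4. If a separate baseline form is 'pre'.** The fall is multiplied by the correlation between the errors of the two forms, which is also assumed. Over the same range of m, s and r:
- independent errors: 0 points, about 5% rejection;
- later day, correlation 0.2 to 0.3: 0.05 to 1.44 points, 5% to 7% (n=20);
- same day, correlation 0.5 to 0.8: 0.14 to 3.83 points, 5% to 19% (n=20).

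**5. If the total is tested.** Selection acts on the nine sensory items. Item 20 is for males, so 19 items can be answered, or 18 by non-drivers. On a simple item average the fall shrinks to 9/19 = 47% or 9/18 = 50% of the values above. In row 1 that is 4.79 × 9/19 = 2.27 points.

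**The case against.** The bias arises only if the calendar prevails, and the text leans the other way: Section 10 names CIPN-20 at baseline, and nothing shows that the sponsor chose the entry score as 'pre'. What the documents establish is one missing calendar mark and an undefined score. That stands, and it is why the claim is conditional.

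The size is also not established. Every input beyond the cut-off is assumed, and the 28% figure needs half of those screened to be excluded. Section 4.1 has oncologists refer women already diagnosed with CIPN, and the coordinator screens them by telephone. Both suggest that few fail the cut-off, which points to the bottom rows of the table. This stands too, although the documents do not settle it.

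A reader might infer that the entry score is certain to be used, or that a false-positive CIPN-20 result is likely. The documents support neither. Nor does Section 7.1 require a baseline CIPN-20 by name; only the Baseline Visit text does. A reader might also take Section 12's item-median imputation to cover a wholly missing baseline form. Section 12 speaks of individual items and does not say so.

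The objection does not remove the contradiction or the undefined 'pre' score. Both are present under every assumption about size, and left as they are, the choice of form and score could be made after the data are seen.

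**Conclusion.** The point holds as a conditional one. The calendar and the Baseline Visit text disagree, and no section names the 'pre' CIPN-20. If the calendar is followed, the CIPN-20 change is biased, and the direction is always toward improvement. The size is unknown. On the assumptions above it runs from negligible (0.3 points, about 5% rejection) to 4.8 points (about 28% at n=20), with the recruitment route favouring the lower end.

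The scope is narrow. BPI, CIPN-R-ODS and MAIA-2 are not used for selection. A reader might extend the bias to the primary feasibility endpoints, but none of them uses the CIPN-20 change; only the count of required forms in the completion endpoint is left open. Even after correction, a single-arm change cannot be attributed to AT. The correction removes one avoidable source of apparent improvement.

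**What to change.** 1. Add CIPN-20 to the Baseline column of the Section 9 calendar, so that it agrees with the Section 10 Baseline Visit.
2. State in Section 12 that CIPN-20 change is measured from this baseline form, completed before the first AT session, and that the screening score serves eligibility only. In the same sentence, name the score tested: sensory subscale or total.
3. When screening and baseline fall on one day, prefer completing the baseline CIPN-20 on a later pre-AT day through REDCap, which Section 10 already allows, where practicable. Otherwise, or wherever the screening score has to serve as 'pre', report how many women this affects and state regression to the mean as a limitation.

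The later day is a preference because its gain over a same-day repeat rests on assumed error correlations.

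**Cost.** One calendar mark, a few sentences, and one repeat of a 20-item form that Section 10 already lists. No visit is added. The form counts toward questionnaire completion. Section 10 places enrolment after the baseline questionnaires, so a form moved to a later day may fall after enrolment and give an enrolled woman one more form to miss.

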1.2 Secondary Objectives and Endpoints

To evaluate the impact of AT on the reported experience of CIPN.

- 1.2.1 To evaluate central pain processing and cortical connectivity in patients with CIPN treated by acupuncture by analyzing fMRI of all participants.
- 1.2.2 To evaluate if there is any change in patient-reported measures from before AT to after study completion.

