While fMRI has not yet been used to evaluate mechanisms of action of AT in the context of CIPN, an increasing number of studies have applied fMRI to investigate AT over a wide range of pain disorders. Stimulation of acupuncture points is associated with overlapping activity in cortical and subcortical brain regions, including the insula, thalamus, anterior cingulate cortex, primary and secondary somatosensory cortices, and deactivation in limbic-paralimbic-neocortical network. Acupuncture can modulate activity within specific brain areas, many of which are known to be important to CIPN pain processing. We hypothesize that regions involved in pain perception will show decreased connectivity between the insula, amygdala and somatosensory cortex with successful pain treatment, with decreased task-related activation of the brain's salience network (anterior cingulate and frontal insula) during mental pain imagery. ¹³⁻¹⁵

Additionally, neurological evidence indicates that some of the brain regions activated during pain perception are also activated when engaging in interoceptive awareness. ¹⁶ Acupuncture has been shown to alter pain processing regions but has not been evaluated regarding changes in mind-body awareness. The possible role of enhanced mind-body awareness as a mechanism of action of acupuncture has not yet been tested. This pilot study will provide a preliminary fMRI and questionnaire data for this topic. Clinical trials of interventions such as mindfulness-based cognitive therapy demonstrate increased interoceptive awareness¹⁷ and decreased depression¹⁸. It seems plausible that AT may provide an opportunity for participants to increase their mind-body awareness while they lie on the treatment table and relax, as well as via neurologic changes in the insula, amygdala, and somatosensory cortex. These regions are known to affect pain processing as well as interoceptive (or mind-body) awareness.

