Functional MRI quantification: Volume and Surface preprocessing pipelines from the Human Connectome Project will be executed for each resting sequence on completion of structural preprocessing. MultiEcho ICA Cleaning: All resting state data will additionally be processed using MultiEcho ICA pipeline (AFNI) allowing removal of non-neural components in the BOLD data. Head motion: Rigorous control of head motion begins before acquisition with subject training and instruction, continues during scanning with repeated reminders to hold still and analysis of image quality after each scan with repetition as possible, and postprocessing including voxelwise despiking, motion parameter estimation and correction, physiologic waveform regression, Multiecho ICA cleaning, and volume censoring (scrubbing). Post-hoc mean and maximal root-mean-square head motion estimates will be used as covariates for all biomarkers. Connectivity: Time series will be estimated FreeSurfer-defined subject-specific regions of interest in somatosensory cortex, anterior cingulate, anterior insula, amygdala, thalamus, medial prefrontal cortex, orbitofrontal cortex, and precuneus, as well as at 361 ROIs for graph-theoretic and network analyses (modularity and clustering coefficient) comprising 333 cortical ROIs strategically positioned at network hubs, 14 cerebellar ROIs, and 14 subcortical gray matter ROIs defined from Freesurfer segmented subject specific nuclei.

Functional MRI Analysis: We will analyze functional connectivity using a parcellation covering the cortical and subcortical gray matter at 5 mm resolution. Brain parcellation will be constructed by assessing regions of interest (ROIs) and measuring each voxel, which can represent a million brain cells. Each voxel will be tested in sequence beginning with the inferior left voxel in the cerebellum. If a voxel is greater than 5 mm distant to voxels already selected, then this voxel will be included in the set of ROI center coordinates.

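### The imaging task needs a painful body part, but women without hand or foot pain can enrol, and the plan does not name, record or repeat the cued site

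*Combined protocol and SAP*

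**What the plan says.** **Task.** Section 10 (Functional MRI) specifies a mental imagery task in 20-second blocks. Visual cues prompt the woman to alternate between "a part of their body where they experience pain and a part of their body where they do not experience pain". There are two scans, one within 9 days after baseline and one within a week of the last acupuncture session.

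**Eligibility.** Under criterion 5.1.4, women "report at least 1 month of altered sensation and/or pain in the feet" and must reach 20 on the 0-100 sensory subscale of the CIPN-20. The Study Summary and the opening of Section 10 also make pain an alternative to altered sensation; Section 10 has "and/or pain with a score of greater than or equal to 20 for CIPN on the sensory subscale".

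**Objective.** Section 1.2.1 sets out to evaluate central pain processing and cortical connectivity "in patients with CIPN treated by acupuncture by analyzing fMRI of all participants".

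**Prediction.** Section 2 expects that successful pain treatment will bring reduced task-related "activation of the brain's salience network (anterior cingulate and frontal insula) during mental pain imagery".

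**Analysis.** In Section 12 the preprocessing pipelines "will be executed for each resting sequence on completion of structural preprocessing", and the analysis paragraph opens: "We will analyze functional connectivity using a parcellation covering the cortical and subcortical gray matter at 5 mm resolution". The anterior cingulate and anterior insula are listed there as regions for connectivity time series. No task contrast is defined.

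**Other pain data.** For the baseline visit, Section 10 states: "Questionnaires (BPI, CIPN-20, CIPN-R-ODS, MAIA-2, Demograhpics) will be completed in person" or by e-mail. The calendar in Section 9 places the CIPN-20 at screening, end of study and week 22.

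**The concern.** The task assumes something that the entry criteria do not guarantee. A woman with numbness or tingling alone has no CIPN pain to concentrate on. Either she has no valid painful condition, or she uses a pain from some other cause. In the second case her scan informs a different question from the one in Section 1.2.1.

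The second gap concerns the comparison over time. The prediction is about change from before to after treatment, and such a change is interpretable only if both scans use the same sites. The plan does not say who chooses the site, whether it must be affected by CIPN, whether it is written down, or whether scan 2 reuses it. In a woman whose pain moves, lessens or resolves, staff could in good faith cue a different place. Her pre/post difference would then mix a change of site with a change in response.

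An analysis model can be written after the scans. A cue that was never recorded, or was changed between scans, cannot be recovered.

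**Working it through.** The plan states no effect size, power or sample size for the task comparison, and the 20 participants are set by budget (Section 4.3). There is no figure to reproduce. The checkable question is whether a woman with no hand or foot pain can be eligible.

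**Inputs (Appendix A and criterion 5.1.4)**
- Nine sensory items: 1-6, 9, 10 and 18, each scored 1 to 4.
- Two of them concern pain: item 5 (hands) and item 6 (feet).
- The threshold is at least 20 on a 0-100 scale.
- Assumption: the usual linear transform, score = 100 × (sum − 9) / 27. Here 9 is the minimum sum and 27 = 9 × 3 is the range.

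**Points needed**
- 5 points above the minimum: 100 × 5/27 = 18.5, not eligible.
- 6 points above the minimum: 100 × 6/27 = 22.2, eligible.

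**One answer pattern without pain.** Foot tingling = 4, foot numbness = 4, and the other seven items, including both pain items, = 1.
- Sum = 4 + 4 + 7 = 15.
- Score = 100 × (15 − 9)/27 = 22.2, eligible.

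**A second, more moderate pattern.** Foot tingling = 3, foot numbness = 3, trouble standing or walking = 3, and the other six items = 1.
- Sum = 9 + 6 = 15, which again scores 22.2.

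**Ceiling without pain.** The seven non-pain items can add at most 7 × 3 = 21 points, so the score can reach 100 × 21/27 = 77.8.

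**Other scoring.** If the score were the item mean × 25, the first pattern would give 15/9 × 25 = 41.7. If it were the raw sum, a woman with both pain items at 1 could reach 2 × 1 + 7 × 4 = 30. Pain is not needed under either.

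**The sections side by side**
1. Section 10 requires a painful and a non-painful body part.
2. Criterion 5.1.4, in both its wording and its score, admits women with neither hand nor foot pain.
3. Section 1.2.1 includes every participant's fMRI.
4. Section 10, the calendar and Section 12 contain no rule for women without a painful site, no requirement that the site be a CIPN site, no field for the cued site and no instruction to reuse it.
5. Section 2 makes a directional prediction about the task, but Section 12 defines no quantity that would test it.

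Items 1 to 3 cannot all be met for a woman with sensory symptoms only, unless she uses pain from another source. Items 4 and 5 mean that nothing elsewhere in the documents closes the gap.

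**The case against.** **The sentence in Section 10 describes a task; it is not an operating rule.** This stands. A reader might infer that a woman whose pain resolves must lose her second scan or be cued elsewhere. The documents do not support that. No section drops a scan for absence of pain, Section 1.2.1 keeps all participants, and the task is imagery, so she can still be asked to concentrate on the foot that used to hurt. The change of site is a possibility left open. The problem for women with no hand or foot pain at entry is firmer, because for them the described condition does not exist at either scan.

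**Other data may fill the gap.** In part they do. CIPN-20 items 5 and 6, collected before and after treatment, can identify women without hand or foot pain. The BPI adds four 0-10 pain items at baseline and end of study. Section 7.1 pairs a study interview with each scan, but its content is not given. None of these is said to record what the woman was cued to.

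**An imaging manual may specify the site.** It may, but the documents cite none. A reference to one would settle the site question, though not the missing contrast in Section 12.

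**This is a small pilot and the aim is secondary.** That limits the weight of the point. However, Section 8 of the argument is the plan's own: Section 2 presents the pilot as groundwork for a randomized trial and names fMRI mechanisms as something to examine, so the task should be defined for everyone who performs it.

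**Conclusion.** The point holds in two parts of different strength.

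- **Mismatch with eligibility.** The task as written is undefined, or unrelated to CIPN, for women who enrol without hand or foot pain. This follows from the text. The scoring example rests on the assumed linear transform, but the wording of criterion 5.1.4 makes pain optional under any scoring.
- **Site not held constant.** The cued site is not tied to CIPN, recorded or repeated, so a pre/post difference could reflect a change of site. This is a risk.

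In addition, Section 12 has no contrast for the salience-network prediction in Section 2.

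The size cannot be given. The documents state neither the share of eligible women without hand or foot pain nor the share whose pain would change or resolve, so any figure for bias or lost power would rest on invented inputs. One eligible pattern without pain is enough to show the mismatch.

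A reader might also infer that the trial's main results are in doubt. They are not. The feasibility endpoints count completed scans, sessions and questionnaires, whatever the cue, and resting-state connectivity does not use the cued site. Only the secondary, preliminary task-fMRI aim is affected. The change is worth making before the first scan, because the cue cannot be reconstructed later.

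**What to change.** **Before scan 1,** record two sites for each woman:
- one CIPN-affected hand or foot site: the most painful one or, if none is painful, the site of the worst CIPN symptom, flagged as non-painful;
- one symptom-free site.

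**At both scans,** name these two sites in the visual cues and use the same two, even if pain has resolved by scan 2.

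**In Section 12,** state the contrast: change from scan 1 to scan 2 in (CIPN site minus symptom-free site), in the anterior cingulate and frontal insula.

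**Analysis set.** Analyse all women, as Section 1.2.1 intends. Also report separately those with and without baseline hand or foot pain, using CIPN-20 items 5 and 6 as already collected. The separate report is needed because the contrast compares pain with no pain only in the first group; in the second it compares a non-painful symptom with none.

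**Cost.** Two extra data fields, revised cue wording and a short addition to Section 12. No new rating, scan, visit or change to eligibility is needed.
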